#### 1 ABBREVIATIONS USED IN THE PROTOCOL

| Abbreviation | Term   |
|---------------------|---|
| ACE                 | Angiostatin-converting enzymes                      |
| AE                  | Adverse Event                                       |
| ARB                 | Angiotensin Resistant II Blockers                   |
| CFR                 | Code of Federal Regulation                          |
| CRT                 | Cardiac Resynchronization Therapy                   |
| EHR                 | Electronic Health Record                            |
| GCP                 | Good Clinical Practice                              |
| GIRB                | Geisinger Institutional Review Board                |
| HBP                 | His-Bundle Pacing                                   |
| HIPAA               | Health Insurance Portability and Accountability Act |
| HOT-CRT             | His-Optimized Cardiac Resynchronization Therapy     |
| IRB                 | Institutional Review Board                          |
| LBB                 | Left Bundle Branch                                  |
| LBBP                | Left Bundle Branch Area Pacing                      |
| LV                  | Left Ventricular Pacing                             |
| NYHA                | New York Heart Association                          |
| PHI                 | Personal Health Information                         |
| RVP                 | Right Ventricular Pacing                            |
| SAE                 | Serious Adverse Event                               |
| WHO                 | World Health Organization                           |

#### 2 BACKGROUND AND SIGNIFICANCE

Physiologic pacing has become rapidly accepted into clinical practice. His bundle pacing (HBP) has recently been incorporated into Guideline document for bradycardia pacing. Advances have been made in physiologic pacing in the form of left bundle branch area pacing (LBBAP). Recent report by Huang et al and others described a novel approach to implanting the Medtronic 3830 lead in the Left bundle branch area via right ventricular, deep septal approach. Early experience suggests that LBB pacing can result in significant improvement in LV function in patients with LBBB and heart failure. Additionally, LBBAP has been shown to be safe, feasible and effective in patients with AV block and superior to right ventricular pacing in observational case-controlled studies. The potential advantage of this method is several fold: 1. Bypass the

IRB NUMBER: 2022-0917 IRB Approved: 04/18/2024

site of conduction block in patients with infranodal AV block and LBBB (even in patients where His bundle pacing fails to correct the LBBB) 2. Achieve low capture threshold with excellent sensing 3. Obtain LV endocardial pacing in addition to conduction system pacing without a lead in the LV endocardial cavity.

The success of LBBAP has been variable between 80-90% based on several observational studies and Geisinger experience. The procedural duration and fluoroscopy duration for LBBAP is somewhat longer than traditional right ventricular pacing. Left bundle branch area pacing (LBBAP) can be challenging in patients where the sheath cannot be oriented perpendicularly to the septum. In some patients, the lead may advance deep into the septum in a tangential fashion. Existing methods have limitations in assessing the exact depth of the lead in the septum and proximity to the LV endocardial surface. We hypothesize based on our early experience that transthoracic echocardiogram including hand-held echo can be helpful in most of the above scenario to both facilitate successful implantation and assessment of the lead location during the implantation and possibly reduce the fluoroscopy duration.

#### 3 OBJECTIVES

#### 3.1 General Objective

The objective of the study is to assess the utility of intraprocedural transthoracic echocardiogram to facilitate successful LBBAP.

### 3.2 Specific Objective

- To assess the success rate of intraprocedural transthoracic echocardiogram guided LBBAP lead implantation.
- To develop a work-flow and define echocardiography windows to achieve successful LBBAP
- To demonstrate reduction in fluoroscopy and procedural duration for LBBAP.
- To assess the success rates of using hand-held echo probe to achieve LBBAP

IRB NUMBER: 2022-0917 IRB Approved: 04/18/2024

#### 4 STUDY DESIGN

## 4.1 Description

The EC-LBBAP study is a prospective, single-center, observational research study. The study team will identify all patients who satisfy the inclusion and exclusion criteria. The study team will evaluate the feasibility and success rates of echocardiogram guided LBBAP lead implantation.

Eligible patients would undergo LBBAP using Medtronic 3830 lead and C315His sheath. LBBAP will be confirmed at implant using left bundle potentials recorded from the lead, ECG morphology during unipolar and bipolar pacing, peak LV activation time and lead depth in the 2D transthoracic echo at implant.

During implant procedure, transthoracic echo windows will be identified and documented: Parasternal short and long axis, apical 2 and 4 chamber views and subcostal views to visualize the proximal interventricular septum. Following venous access using cephalic vein cut-down or ultrasound guided axillary vein access, the lead implantation in the left bundle branch region will be guided by echocardiography.

Retrospectively, the study team will identify 30 consecutive previous patients who satisfy inclusion and exclusion criteria (control patients). The study team will compare the difference in procedural success between Case and Control patients.

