#### Visit 1 – Baseline

The following activities will be completed at Visit 1 (Baseline):

• Subjects will be screened to ensure they meet ALL the inclusion criteria and NONE of the exclusion criteria.

IRB NUMBER: 2022-0917 IRB Approved: 04/18/2023

- Subjects will sign an Informed Consent form before any of the study related procedures are performed.
- Demographic
- Medical history
- Concomitant medication specifically ACE/ARB, beta blockers, diuretics, and antiarrhythmics use
- Relevant co-morbidities will be recorded
- NYHA Functional Classification
- Collection of device characteristics and implanted system description.
- EC-LBBAP research procedure \*

Intraprocedural transthoracic echocardiogram\*

Fluoroscopy duration for LBBAP lead implantation

Procedural duration for LBBAP lead implantation

Total fluoroscopy duration

Total procedural duration

Success of LBBAP

- 12-lead ECG (Rhythm Strips)
- Adverse Events related to echocardiogram

\*The use of the EC-LBBAP may add approximately 15 minutes of time for total procedure but may lower the fluoroscopy and procedure duration for LBBAP lead implantation. Additionally, this may improve the safety and success of the procedure.

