#### 4.6 Primary Endpoints

The primary endpoints will be

- Success rate of LBBAP utilizing intraprocedural transthoracic echocardiogram
- Reduction in fluoroscopy/procedure duration for LBBAP lead implantation compared to historic data from prior Geisinger studies utilizing LBBAP
- Identification of work-flow and echocardiographic windows to facilitate LBBAP

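### Success is undefined, and if lead depth on the study echo counts toward it, the Section 4.1 comparison may judge cases and controls by different tests

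*Combined protocol and SAP*

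**What the plan says.** Section 4.1 lists four kinds of evidence that confirm LBBAP at implant: left bundle potentials from the lead, ECG morphology during unipolar and bipolar pacing, and "peak LV activation time and lead depth in the 2D transthoracic echo at implant". It sets no cut-off for any of them and does not say whether all, some or any one must be met.

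The same section identifies 30 consecutive previous patients as controls and states: "The study team will compare the difference in procedural success between Case and Control patients". It does not say whether procedural success means the four items just listed.

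Section 4.5 (Visit 1 – Baseline) places the intraprocedural echo under the "EC-LBBAP research procedure" and lists success of LBBAP as a data item, without a definition. Section 4.6 names "Success rate of LBBAP utilizing intraprocedural transthoracic echocardiogram" as the first primary endpoint, also without a definition. The historic comparison in 4.6 concerns durations only: "Reduction in fluoroscopy/procedure duration for LBBAP lead implantation compared to historic data from prior Geisinger studies utilizing LBBAP".

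Section 2 gives the background rate: "The success of LBBAP has been variable between 80-90% based on several observational studies and Geisinger experience". It does not state the criteria behind that range.

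**The concern.** A comparison of success rates needs the same test of success in both groups. Here one of the four confirming items comes from the study echo. The protocol does not say that controls had that echo or any equivalent depth measure. If depth enters the success call, cases could be scored on four items and controls on three.

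The direction depends on a rule that is not stated. If depth is required, a case that meets the electrical criteria can still fail, so cases face a stricter test. If depth can tip a case to success, alone or as one of several items under a rule such as any two of four, cases face a more lenient test. In that situation the tool that guides the implant also helps to certify it, and the 4.6 single-arm rate rises as well.

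The stake is the pilot's own purpose. Section 4.8 says the results will be used to design a larger study. A success rate or difference whose meaning depends on an unstated rule is a poor planning input.

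**Working it through.** **Reading.** The protocol has no sample-size, power or alpha statement, so there is no figure of its own to reproduce. Every section that mentions success or confirmation was checked (2, 3.2, 4.1, 4.5, 4.6, 4.8). None gives a cut-off, a combining rule, or a definition common to both groups. Section 2 bears on whether controls have a depth measure, and it points both ways:

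- "We hypothesize based on our early experience that transthoracic echocardiogram including hand-held echo can be helpful": the site had used echo before, so some earlier patients may have a depth reading.
- "Existing methods have limitations in assessing the exact depth of the lead in the septum": outside the study echo, depth was hard to judge, so a comparable measure in most controls is doubtful.

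**Illustration of size.** Inputs from the documents: about 30 cases (4.2.1), 30 controls (4.1), background success of 80% to 90% (Section 2). Assumptions: echo has no true effect, both groups have success probability p on the non-echo criteria, and depth reclassifies a share q of cases. The values of q are assumed; nothing in the documents supports them.

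- Depth can tip a case to success, with q the share of electrical failures counted as successes: case rate = p + (1 − p)q.
- Depth is required, with q the share of electrical successes rejected: case rate = p(1 − q).
- 95% half-width of the difference: 1.96 × √[p₁(1 − p₁)/30 + p₂(1 − p₂)/30].

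| Rule | p (controls) | q | Case rate | Artefact (points) | Half-width (points) |
|---|---|---|---|---|---|
| Can tip | 80% | 0.50 | 90% | +10 | 17.9 |
| Can tip | 80% | 0.25 | 85% | +5 | 19.2 |
| Can tip | 90% | 0.50 | 95% | +5 | 13.3 |
| Can tip | 90% | 0.25 | 92.5% | +2.5 | 14.3 |
| Required | 80% | 0.10 | 72% | −8 | 21.5 |
| Required | 80% | 0.05 | 76% | −4 | 20.9 |
| Required | 90% | 0.10 | 81% | −9 | 17.7 |
| Required | 90% | 0.05 | 85.5% | −4.5 | 16.6 |

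With no artefact, the half-width is 1.96 × √(2 × 0.16/30) = 20.2 points at 80% and 1.96 × √(2 × 0.09/30) = 15.2 points at 90%.

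Larger assumed shares give larger artefacts. With q = 0.75 and p = 80%, tipping gives 0.80 + 0.20 × 0.75 = 95% (+15). With q = 0.20 and p = 90%, a required depth gives 0.90 × 0.80 = 72% (−18). The half-widths for these two pairs, 16.3 and 19.3 points, still exceed the artefact.

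**Effect on what would be seen (exact binomial enumeration, 30 versus 30).** The two-sided Fisher rejection rate at an assumed 0.05 is 2.2% for 80% versus 80%, 9.6% for 90% versus 80%, and 6.5% for 72% versus 80%. The chance that cases appear at least 10 points better (3 patients of 30) is 20.9%, 57.1% and 6.8% for the same pairs. The 57.1% should not be over-read, because the 10-point threshold equals the artefact assumed.

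**The case against.** The strongest reply is that only the lack of a definition is certain. Section 4.1 says how pacing is confirmed at implant; it never equates this with procedural success, and 4.5 lists success as its own item. A reader might infer that the four items are the endpoint and that controls had no echo. The documents establish neither, and limited depth assessment is not absent depth assessment. This stands, and it is why the point is conditional.

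A reader might also infer that the bias affects a primary comparison. It does not: the success contrast appears only in 4.1, the 4.6 historic comparison covers durations, and 4.8 calls test results not conclusive.

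The list in 4.1 is joined by the word and, so depth sufficing alone is the less natural reading. That is fair, but inflation does not need depth to suffice alone. Any rule that lets depth supply the last item needed has the same effect.

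It is tempting to set the +10 and −8 results at 80% against each other and report an 18-point swing. Those are two mutually exclusive rules under chosen shares, and no single analysis would show that difference.

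Finally, sampling error exceeds the artefact in every scenario shown. That is true, but sampling error is visible in a confidence interval and shrinks with sample size. A difference in definition is not visible there and would carry into the larger study.

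**Conclusion.** The point holds in conditional form. It is certain that success has no cut-offs, combining rule or common definition, although it is the first primary endpoint and the subject of the 4.1 comparison. It is conditional that the groups would be judged by different tests: this requires that depth counts toward success and that controls lack a comparable depth measure.

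The direction is unknown because the rule is unstated, and the size is unknown because the documents give no reclassification rates. Under the assumed shares in the table each artefact is about 2.5 to 10 points, against a half-width of about 15 to 20 points when both groups truly succeed at 90% or 80%.

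No confirmatory error rate is at stake, and the harm is confined to interpreting the pilot and planning the next study. The change should be made because it is cheap and concerns a primary endpoint, but it does not undermine the study.

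**What to change.** In Sections 4.1 and 4.6, state one definition of success based on the non-echo criteria: left bundle potential, paced ECG morphology and peak LV activation time. The investigators should set the cut-offs and the combining rule. Use this definition for both the 4.6 success rate and the 4.1 comparison, and apply it identically to case and control records.

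Report echo lead depth in cases separately. If the investigators want success including depth, give it as a supplementary figure labelled as case-only.

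The cost is protocol wording and extra chart abstraction, which 4.9.1 already allows through manual chart review. The real downside is that some controls may have incomplete tracings. Report how many, with a best-case and worst-case range for the control rate. Each such control widens that range by 1/30 = 3.3 points, so 3 controls give 10 points and 6 give 20. That can match or exceed the artefact being removed, but it is reported openly, whereas a mismatch in definitions is not.

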## 4.9 Data Management

### 4.9.1 Data Collection and Storage

Data will be collected by research team members, and the resulting analytic file will be stored in a password-protected database on Geisinger's secure network. Only research team members can access the data file. The research team members will review the charts and gather all the needed information. The research team plans to perform manual chart reviews to access any required data elements

The following data, including relevant dates, will be collected:

- Medical record number
- Date of birth/date of death
- Information relevant to all encounters, admissions/discharges, clinical procedures, medications administered, problem list entries, and lab values
- Baseline demographic variables of patients (age, sex, ethnicity, tobacco use, comorbidities)
- Clinical outcomes and procedural related complications

All identifiable date will be stored on a secure server in password protected files. Any hard copy data will be secured in a locked (area/suite/drawer/cabinet), if applicable. Only aggregate data (i.e., no PHI) will be shared with the Sponsor.

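### The implanting operator is not a named data item and the comparators are earlier implants, so operator mix or growing LBBAP experience could bias the success and duration comparisons

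*Combined protocol and SAP*

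**What the plan says.** Two comparators are described, both earlier than the echo cases.

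- **Success (section 4.1).** The controls are defined thus: "Retrospectively, the study team will identify 30 consecutive previous patients who satisfy inclusion and exclusion criteria (control patients". Eligibility is the only selection rule; no operator, matching factor or calendar window is given. The next sentence states their use: "The study team will compare the difference in procedural success between Case and Control patients".
- **Duration (section 4.6).** A primary endpoint reads "Reduction in fluoroscopy/procedure duration for LBBAP lead implantation compared to historic data from prior Geisinger studies utilizing LBBAP". The documents do not say whether these historic data are the 30 controls of section 4.1.

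Section 3.2 gives the matching aim: "To demonstrate reduction in fluoroscopy and procedural duration for LBBAP".

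The Visit 1 list in section 4.5 records lead and total durations, such as "Fluoroscopy duration for LBBAP lead implantation", and LBBAP success. It does not list the operator. Section 4.9.1 lists "Baseline demographic variables of patients (age, sex, ethnicity, tobacco use, comorbidities" among its items and, more broadly, "Information relevant to all encounters, admissions/discharges, clinical procedures, medications administered, problem list entries, and lab values", with relevant dates, obtained by manual chart review. The operator and the operator's experience are not named there either.

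Section 4.8 plans chi-square or Fisher tests and t-tests or rank-type tests. It has no stratum, covariate or time trend. It also says that test results are not conclusive and will serve to design a larger study.

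**The concern.** How long an LBBAP implant takes, and whether it succeeds, can depend on who implants and on how many such leads that person has placed. Section 2 itself calls the approach novel and sometimes challenging. If the cases have a different operator mix from the comparators, or the same operators have become more practised, an unadjusted comparison credits that difference to echo guidance.

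At stake are one primary endpoint (duration), the case-control comparison of success, and the effect estimates that would be carried into the larger study.

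**Working it through.** **Inputs from the documents.** About 30 cases (20 standard echo + 10 hand-held, section 4.2.1) and 30 controls (section 4.1). No alpha, power, SD, effect size or duration is given, so there is no plan figure to reproduce.

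**Assumptions.** Two-sided 5% test, duration analysed on the log scale with SD 0.4 to 0.6, all 30 cases against 30 comparators, and no true echo effect.

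**1. Chance of a spurious finding.** The standard error is SE = SD × √(2/30), which is 0.103, 0.129 and 0.155 for SD 0.4, 0.5 and 0.6. A spurious reduction r is a log shift d = −ln(1 − r): 0.105, 0.223 and 0.357 for 10%, 20% and 30%. The rejection probability is Φ(d/SE − 1.96) + Φ(−d/SE − 1.96).

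| Spurious reduction | SD 0.4 | SD 0.5 | SD 0.6 |
|---|---|---|---|
| 10% | 18% | 13% | 10% |
| 20% | 58% | 41% | 30% |
| 30% | 93% | 79% | 63% |

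The nominal rate is 5%.

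**2. What could produce such a shift.** All inputs here are assumed.

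- *Operator mix:* the reduction is 1 − exp(−L × s), where L is the log ratio between operators and s the change in the faster operator's share. L = 0.2 to 0.4 means 18–33% faster. With s = 0.3 this gives 1 − exp(−0.06) = 6% to 1 − exp(−0.12) = 11%. With a single operator it is zero.
- *Experience:* the reduction is 1 − (1 − q)^t for a yearly fall q over a gap of t years. q = 5% and t = 1 gives 5%; q = 15% and t = 3 gives 1 − 0.85³ = 39%. The top of this range needs both extremes.

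**3. What recording the operator gains.** In a simulation (two operators, 30 v 30, 4,000 runs per scenario, no echo effect), significant results favouring echo, nominally 2.5%, were as follows.

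| Operator gap | Faster operator's share, controls → cases | Unadjusted t-test | Operator in model |
|---|---|---|---|
| 1 SD | 30% → 70% | 28% | 2.8% |
| 1 SD | 20% → 80% | 57% | 2.7% |
| 1.5 SD | 30% → 70% | 47% | 2.4% |

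The gaps and shares are assumptions, and the share shifts are larger than in step 2. Adjusting for operator does not remove learning within an operator.

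**4. Whether a trend in the controls can rule out learning.** With 30 controls spread evenly over one year, the sum of squares of time is 30 × 1/12 = 2.5. At log-SD 0.5 the slope SE is 0.5/√2.5 = 0.32 per year. A 15% yearly fall is a slope of 0.163, about half an SE. Power is about 5% for a 5% yearly fall and 8% for a 15% fall. Over two years (SE 0.16) it is about 6% and 18%. A flat slope would therefore say little.

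**The case against.** The strongest case against has five parts.

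- **The operator can be recovered.** A reader might infer that the operator is lost for good and that no later analysis could correct for it. The documents do not support that. Chart review under section 4.9.1 covers clinical procedures and relevant dates, the medical record number is kept, and records are held for at least 6 years (section 4.9.2). The gap is an unnamed field. Dates, and so procedure order, need no new item.
- **No time gap is shown.** A reader might set the 2019–2021 site reports in the reference list against the 2023–2024 approval stamps and infer a gap of years. Those reports are background citations, and nothing says they supply the controls. The consecutive earlier patients of section 4.1 could be those immediately before the study.
- **No operator difference is shown.** This is a single-center study, and the documents do not say how many operators implant.
- **The direction is not fixed.** A reader might infer that the bias must favour echo. Growing LBBAP experience would push that way, but operator mix can shift either way. The echo workflow is still being developed (section 3.2), and the Visit 1 note allows about 15 extra minutes of total procedure time, so unfamiliarity with echo could lengthen procedures.
- **The tests are declared not conclusive (section 4.8).** This lowers the severity. It does not remove bias from an estimate meant to design the next study, and it sits uneasily with the aim in section 3.2 to demonstrate a reduction.

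The first four limit how strongly the point can be put. What remains is that nothing in the plan separates echo guidance from who implanted and with what experience.

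**Conclusion.** The point holds as a cheap and worthwhile improvement. Both comparators are earlier implants, the operator is not a named item, and the planned tests are unadjusted, so the plan as written can attribute an operator or experience difference to echo.

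The bias is possible, not demonstrated, and its likely direction is towards echo without being certain. The rejection rates in the first table rest on the assumed log-SD and spurious reductions, not on trial data, and they concern duration only. The success comparison has the same weakness, but no size is computed for it here.

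**What to change.** 1. State that the section 4.1 controls are also the comparator for the duration endpoint in section 4.6, or otherwise reconcile the two sections. Without this, a better control rule may miss the endpoint it is meant to protect.
2. Name a coded implanting operator as a data item for cases and controls, taken from the implant report. Derive procedure order from the implant dates already collected.
3. Define controls as the most recent consecutive LBBAP attempts before the first echo case by the operators who implant the cases.
4. Report the duration and success differences stratified by or adjusted for operator, with confidence intervals, next to the unadjusted result.
5. Show duration against procedure order descriptively only. Do not read a flat slope in 30 controls as evidence against learning, and state residual learning or calendar effects as a limitation.

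The cost is one chart field, a slightly more complex control selection and a few degrees of freedom.
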